5.6. Exploratory Endpoints Analysis for the LTE Period

- Proportion of participants achieving GC-free remission from Week 52 (LTE Week 0) through Week 104 (LTE Week 52) by visit
- Time to first GCA disease flare discontinuation of study intervention due to AE of worsening of GCA from Week 52 (LTE Week 0) through Week 104 (LTE Week 52)
- The number of GCA disease flares or discontinuation of study intervention due to AE of worsening of GCA from Week 52 (LTE Week 0) through Week 104 (LTE Week 60) by visit
- Change from baseline in ESR from Week 52 (LTE Week 0) through Week 104 (LTE Week 52) by visit
- Proportion of participants with normalization of ESR from Week 52 (LTE Week 0) through Week 104 (LTE Week 52) by visit
- Change from baseline in CRP from Week 52 (LTE Week 0) through Week 104 (LTE Week 52) by visit
- Proportion of participants with normalization of CRP from Week 52 (LTE Week 0) through Week 104 (LTE Week 52) by visit

Patient-reported Outcomes by visit at Weeks 52, 76, and 104

- Change from baseline in PGA.
- Change from baseline in Pain Severity Assessment.
- Change from baseline SF-36 PCS (physical component summary) score and MCS (mental component summary) score.
- Change from baseline in SF-36 individual domains.
- Change from baseline in FACIT-fatigue scale score (raw score).
- Proportions of participants with FACIT-fatigue scale score ≥ 40 (mean= 40, SD=10).

- Proportions of participants with \geq 4-points improvement in FACIT-fatigue scale score (raw score).

Physician-reported Outcomes

- Change from baseline in PhGA.

5.6.1. Definition of Endpoints

5.6.1.1. GC-free Remission at Each Timepoint from Week 52 through Week 104

1. No signs or symptoms of active GCA at timepoint Week X
AND
2. Absence of GCA flare from first dose of the study agent from Week 52 through Week X

5.6.2. Analysis Methods

The analysis population will be participants who enter into the Long-Term Extension. The endpoints will be summarized by intervention group.

The Treatment Policy strategy will be applied to the binary exploratory secondary endpoints (proportion of responders). For participants who experience an intercurrent event from Week 52 through Week 104, the analysis will be performed using observed data regardless of intercurrent events. Missing data will not be imputed.

The survival curves will be estimated using Kaplan-Meier estimates for time to first GCA disease flare or discontinuation of study intervention due to AE of worsening of GCA from Week 52 through Week 104.

Simple descriptive statistics, such as n, mean, SD, median, IQ range, minimum and maximum for the continuous variables over time. The remaining missing data will not be imputed.

The efficacy data during the LTE period will be summarized and displayed by the following intervention groups:

1. Placebo
2. Guselkumab

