If a participant is in GC-free remission at Week 48, the participant will be informed of the possibility to participate in the LTE period and continue to receive study intervention. Study intervention will continue to be blinded, meaning that a participant will continue to receive the treatment that had been allocated to that participant (placebo or guselkumab) in the main study. After the Week 52 evaluations, if the participant is eligible and has consented for the LTE, the participants will continue to receive SC study intervention every 4 weeks starting at Week 52 (LTE Week 0) under this protocol's study extension until participants reach Week 100 (LTE Week 48) or until a participant experiences a GCA flare, or the participants discontinues treatment due to unblinding after the Week 60 DBL for the Main study, or until the Sponsor makes a decision not to continue this study, whichever occurs first. Participants who continue treatment as part of the study extension will be intermittently evaluated per the protocol for efficacy, PK, and safety. The LTE period is followed by a 12-week safety follow-up period after the last dose (a final efficacy visit 4 weeks after the last dose and a safety follow-up visit 12 weeks after the last dose). Participants that experience a flare should have have a Flare visit with assessments performed according to the SoA preferably within 1 week of having the flare and an early termination visit approximately 12 weeks after the last dose. In case a participant is diagnosed as having a flare during a study visit or shortly before a planned study visit, the Flare visit and regular visit can be combined. Overlapping procedures and assessments need only be performed once. The FDG-PET/CT scan can be scheduled separately from other assessments.

After the Week 60 DBL, the study will be unblinded to treatment. Any participants in the LTE that are on placebo will be informed and administration of study intervention will be discontinued. The participants may still continue in the study until Week 112 or until the end of the safety follow-up period in case they experienced a GCA flare.

A diagram of the study design is provided in Section [1.2](#).

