- The participant has a serious adverse reaction that is related to an injection resulting in bronchospasm with wheezing and/or dyspnea that requires ventilatory support OR that results in symptomatic hypotension with a decrease in systolic blood pressure >40 mm Hg or blood pressure $<90/60$ mm Hg
- The participant has a reaction resulting in myalgia and/or arthralgia with fever and/or rash (suggestive of serum sickness and not representative of signs and symptoms of other recognized clinical syndromes) occurring 1 to 14 days after an injection of study intervention. These may be accompanied by other events including pruritus, facial, hand, or lip edema, dysphagia, urticaria, sore throat, and/or headache

- The participant has a malignancy including squamous cell skin cancer. Consideration may be given to allowing participants who develop ≤ 2 basal cell skin cancers that are adequately treated with no evidence of residual disease to continue to receive study intervention
- Participant requires dialysis
- Noncompliance with study drug administration defined as multiple episodes of missing the window in which to receive study intervention
- The participant has severe liver test abnormalities that are not transient and are not explained by other etiologies, as described in Section 10.9.
- In the LTE period, the study intervention must be discontinued if a participant experiences a GCA flare. Participants that experience a flare should have a Flare visit with assessments performed according to the SoA preferably within 1 week of having the flare and an early termination visit approximately 12 weeks after the last dose.
- After the study has been unblinded at the Week 60 DBL, participants in the LTE will be unblinded to treatment. Study treatment of participants on placebo will be discontinued. They may continue in the study for their planned visits as per the schedule of events until Week 112 or, in case of a GCA flare, until the early termination visit.

Discontinuation of a participant's study intervention should be considered under the following conditions:

- Worsening of GCA based on visual symptoms related to GCA
- If the participant initiates treatment with prohibited therapies for GCA, the medical monitor or designee should be contacted to discuss possible discontinuation of study intervention
- The participant develops a serious infection, including but not limited to sepsis or pneumonia

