3. SAMPLE SIZE DETERMINATION

Approximately 51 participants are planned to be randomized into the study. The assumptions for the sample size and power calculation were based on the data from the Actemra Phase 3 GCA study. In the Actemra Phase 3 study, the proportions of participants in GC-free remission at Week 28 were estimated to be approximately 38% and 74% for placebo (+26-week GC taper) and Actemra qw (+26-week GC-taper), respectively, for a treatment difference of 36%.

Based on the data above, the GC-free remission rates at Week 28 are assumed to be 40% for placebo and 80% for guselkumab treatment arm. Based on these assumptions, 51 participants are planned to be randomized in a 2:1 ratio to either the guselkumab group (N=34) or the placebo

group (N=17). These sample sizes provide the study with 82% power to detect a difference in the primary endpoint between the 2 study intervention groups.

Table 1 shows the power to detect a difference in proportions of participants in GC-free remission between the guselkumab and placebo intervention groups at Week 28 under various assumptions.

Table 1: Power to Detect Difference in Proportions of Participants Achieving Glucocorticoid-free Remission between the Guselkumab and Placebo Intervention Groups at Week 28

Placebo (n = 17)	Guselkumab (n = 34)	Power (%)
35%	70%	68
	75%	81
	80%	90
40%	75%	69
	80%	82
	85%	91

Notes:

- The power calculation is based on two-sample Z test with continuity correction (pooled variance) under the normal distribution approximation.
- Power calculation is based on a 2-sided significance level of 0.10.
- Total sample size is 60.

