5.3.1. Definition of Endpoint

GC-free remission response at Week 28 is defined as:

1. No signs or symptoms of active GCA at Week 28
AND
2. Absence of GCA flare from first dose of the study agent through Week 28,
AND
3. Adherence to the protocol specified 26-week GC taper

Definition of GCA Flare: GCA flare is defined as the recurrence of signs and symptoms of active GCA, with or without elevation of inflammatory markers, and with the necessity for an increase in GC dose for GCA.

Having CRP/ESR elevations in isolation without clinical signs and symptoms attributable to GCA, does not qualify as flare, unless the investigator decided to increase the GC dose.

Definition of GC Taper Adherence. The protocol specified 26-Week open-label GC tapering schedule is provided in Section 10.8 of the protocol. Adherence to this schedule is required. Participants will remain on the GC dose they were on at baseline for one week (Week 0). The taper is starting at Week 1 and continues down to GC-free in Week 26, as per the schedule. Participant should adhere to the tapering schedule through Week 26 unless they require use of rescue GC therapy for GCA disease flare.

A participant will be considered as not adherent to the protocol-defined 26-week GC taper, if the compliance of GC intake (any oral GC intake) is greater than 120% cumulative prednisone (or equivalent) dose, between first and last planned dose of GC taper. Patients not adhering to the GC

taper will be considered as non-responders in the primary analysis. Participants receiving less than the planned amount of prednisone (or equivalent) will not be considered as non-responders.

Compliance of GC intake will be calculated as follows:

Compliance (%) = (actual GC dose taken/total GC dose supposed to be taken) x100.

If a participant receives GC other than prednisone or prednisolone, the amount of GC dosage equivalent to prednisone recorded on Concomitant Therapy page in the eCRFs will be converted to a prednisone-equivalent dose using the following table.

GC	Conversion factor from alternative GC to prednisone equivalent dose (mg)
Cortisone acetate	0.2
Hydrocortisone	0.25
Deflazacort	0.67
Prednisone	1
Prednisolone	1
Triamcinolone	1.25
Methylprednisolone	1.25
Dexamethasone	6.67
Betamethasone	6.67

The following rules will be used to assess a GC-free remission at Week 28:

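### SAP 5.6.2 displays LTE remission, flares and global assessments by arm over Weeks 52-104 without separating assessments made before and after the Week 60 unblinding

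*SAP*

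**What the plan says.** The blind ends on one calendar date for the whole trial. Protocol 6.3 keeps sites and participants blinded until the Week 60 database is locked. Protocol 4.1 says of the LTE: "After the Week 60 DBL, the study will be unblinded to treatment". Those in the placebo group learn their assignment at that point, and Protocol 7.1 states: "Study treatment of participants on placebo will be discontinued". Follow-up of this group can still run to Week 112. No such stop applies to guselkumab, so those participants continue with the arm known.

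SAP 5.6 lists the LTE efficacy endpoints: GC-free remission by visit, time to first flare (or discontinuation for worsening GCA), number of flares, ESR and CRP, PhGA, and the patient-reported outcomes. Binary endpoints follow a treatment policy rule, which SAP 5.6.2 states: "For participants who experience an intercurrent event from Week 52 through Week 104, the analysis will be performed using observed data regardless of intercurrent events". Time to first flare comes in a separate paragraph, with Kaplan-Meier curves covering Weeks 52 to 104, and continuous variables get descriptive statistics. Everything is displayed as Placebo and Guselkumab. The section has no censoring, flag or split at unblinding.

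SAP 5.3.1 defines a flare as recurrent signs and symptoms "with the necessity for an increase in GC dose for GCA". A rise in CRP or ESR alone also counts if the investigator decides to raise the GC dose. LTE remission (SAP 5.6.1.1) is absence of signs or symptoms at the visit plus absence of flare.

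**The concern.** The protocol uses blinding to limit bias in how endpoints are collected and judged. That protection ends part-way through the LTE for anyone still in follow-up at the Week 60 lock, yet the SAP treats all LTE time alike. The exposed endpoints depend on judgement: whether symptoms are due to GCA, whether more GC is needed, and how the physician and patient rate disease activity. An investigator who knows that a participant has stopped placebo could read ambiguous symptoms as a flare sooner than one who knows that the participant is on active drug.

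At stake is how the LTE display will be read. It answers the exploratory objective on long-term efficacy. A reader who sees Placebo and Guselkumab columns running to Week 104 could take them as blinded, placebo-controlled evidence throughout. Unblinded time also falls on the later LTE visits of those who have it, which is where durability is judged.

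**Working it through.** **1. The plan's own figure.** The documents give no sample size, test or power for the LTE. The one stated power is for the primary endpoint: "These sample sizes provide the study with 82% power to detect a difference in the primary endpoint between the 2 study intervention groups". Inputs from SAP section 3 are 17 placebo and 34 guselkumab, rates of 40% and 80%, two-sided alpha 0.10, and a Z test with pooled variance and continuity correction.
- Pooled rate = (17×0.40 + 34×0.80)/51 = 0.667
- Null SE = √[0.667×0.333×(1/17 + 1/34)] = 0.140
- Alternative SE = √(0.24/17 + 0.16/34) = 0.137
- Correction = 0.5×(1/17 + 1/34) = 0.044
- Power = Φ[(0.40 − 0.044 − 1.645×0.140)/0.137] = 82.0%

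The figure reproduces. This point does not touch it; only the planning rates are used again, in step 4.

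**2. How much LTE time falls after unblinding.** The documents give neither the accrual length nor the lag from the last participant's Week 60 visit to the lock, so both are assumptions: lag L weeks, and LTE entrants accrued evenly over E weeks. A participant randomised u weeks before the last one is at study week 60 + L + u when the lock occurs. Unblinded weeks up to Week 104 are max(0, 44 − L − u). With W = 44 − L, and W no larger than E:
- share of LTE participants with any unblinded time = W/E
- share of planned LTE weeks unblinded = W²/(2 × E × 52)

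With L = 4 and E = 104: W = 40, 40/104 = 38%, and 1600/10816 = 15%. With L = 8 and E = 104: W = 36, 36/104 = 35%, and 1296/10816 = 12%.

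| Lock lag L | Last entrant's unblinded weeks (of 52) | E = 52: participants / weeks | E = 104: participants / weeks | E = 156: participants / weeks |
|---|---|---|---|---|
| 0 | 44 (85%) | 85% / 36% | 42% / 18% | 28% / 12% |
| 4 | 40 (77%) | 77% / 30% | 38% / 15% | 26% / 10% |
| 8 | 36 (69%) | 69% / 24% | 35% / 12% | 23% / 8% |
| 12 | 32 (62%) | 62% / 19% | 31% / 9% | 21% / 6% |

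**3. What moves these shares.** They assume that every entrant is followed to Week 104, with no flare or dropout. A flare in the LTE stops study treatment and leads to an early termination visit (Protocol 4.1 and 7.1), and placebo participants need not stay after unblinding, so for a given L and E the realised shares should be lower. In the other direction, LTE entrants complete the main study at Week 52 (Protocol 4.4). If the last participants all entered the LTE, the lock could come sooner; an 8-week lag counted from Week 52 is the L = 0 row.

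**4. Participants.** If the planning rates held to Week 52 and everyone eligible entered, there would be 0.40×17 = 6.8, about 7 placebo, and 0.80×34 = 27.2, about 27 guselkumab entrants. With 104-week accrual, 35-38% of 7 is 2 to 3 placebo participants with any unblinded time; with 52-week accrual, 69-77% of 7 is about 5. One flare call among 7 moves the placebo remission rate by 1/7, about 14 percentage points.

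**5. Whether another section closes the gap.** Unblinding is not an intercurrent event in SAP 5.3.2.1. Stopping placebo at unblinding would fit the fourth category there, discontinuation for other reasons, which is also treatment policy. SAP 5.2 plans a listing of unblinded participants but does not link it to LTE efficacy. Neither document says that the Clinical Assessor stays blinded after the Week 60 lock.

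**The case against.** The strongest reply is that nothing inferential is planned here. SAP 5.6.2 specifies summaries and Kaplan-Meier curves, with no test, hazard ratio or confidence interval, and the LTE efficacy objective omits the comparison with placebo that the main-study objectives state. Treatment policy on observed data is a legitimate choice for a descriptive extension. All of this stands and sets the priority low.

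Second, the LTE is not a randomised comparison even while blinded. Entry requires no signs or symptoms at Week 52, a completed taper without rescue, and no flare (Protocol 5.1, criterion 19). This also stands: separating the data at unblinding would not yield a valid causal contrast. It removes one avoidable problem, and the selection should be stated.

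Third, the affected share may be small. The protocol's amendment history reports slow enrolment in September 2021, and the sample size was later cut for timely completion, which points away from a 52-week accrual. This is fair, and it is why the table runs to 156 weeks.

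A reader might go further and infer that the LTE result is a biased comparison in guselkumab's favour. The documents do not support that. The direction is plausible but not shown, and flare ordinarily needs recurrent signs and symptoms, assessed against a listed set by a dedicated assessor. A reader might also think that stopping placebo itself distorts the control group. Withdrawing an inert injection changes no drug exposure; what matters is knowledge of the arm.

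**Conclusion.** The point holds as a low-priority gap in the LTE displays. Blinded and post-unblinding assessments are pooled by arm with no rule to tell them apart, and the endpoints depend on judgement. The quoted sentence governs the binary endpoints only; for time to flare and the continuous measures, the gap is that the section is silent.

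With a 4-8 week lock lag and no flare or dropout (both assumptions), about 12-15% of planned LTE weeks would be unblinded with 104-week accrual and 24-30% with 52-week accrual. Longer accrual lowers this, to 8-10% at 156 weeks. In absolute terms few placebo participants are involved, out of about 7 entrants if the 40% planning rate held. Early enrollees may finish Week 104 fully blinded.

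The primary, secondary and Week 52 results are not affected, because sites and participants stay blinded until the Week 60 lock.

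**What to change.** In SAP 5.6.2, before the final database lock:
- Censor time to flare at the participant's unblinding date in the main LTE display.
- Limit the by-arm displays of remission, flare counts, PhGA and patient-reported outcomes to assessments before that date.
- Show later assessments separately, labelled 'guselkumab open-label' and 'placebo stopped'.
- Keep the present all-data display as supportive.
- State that LTE by-arm displays are descriptive, because entry is selected on remission at Week 52.

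The cost is a few sentences and one date variable. No clinical rule, sample size or power changes, and no collected data are discarded. The downside is fewer participants at late LTE visits in the main display, which will be felt most in the small placebo group.

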5.7. Safety Analyses

All safety analyses for the main study will be based on the safety analysis set based on actual intervention received, unless otherwise specified. Safety analyses for the long-term extension will include participants who complete the Week 52 visits and are assessed to be in GC-free remission with at least one SC injection at Week 52 or later.

For all continuous safety variables, descriptive statistics by intervention group will include the N, mean, standard deviation, median, minimum, and maximum. Categorical variables will be summarized by intervention group using frequency counts and percentages.

Depending on the safety data, the cumulative safety data will be analyzed through different study periods which include but are not limited to through Week 28 and through Week 60 for the main study. The safety analyses through Week 60 for the main study will include safety data through Week 60 for participants not entering the LTE and safety data through Week 52 for participants continuing onto the LTE. Safety analyses from Week 52 (LTE Week 0) through Week 112 (LTE Week 60) will be performed for participants in the LTE period.

